5.8.3 North Star Ambulatory Assessment

The NSAA consists of 17 activities, each scored as 0, 1, or 2. The sum of these 17 scores will be used to form a total score. If fewer than 13 of the 17 activities are performed, the total score will be considered missing. If from 13 to 16 activities are performed, the total score will be calculated by multiplying the sum of the scores in the x activities that were performed by $17/x$. If an activity cannot be performed due to disease progression/loss of ambulation, a score of zero will be assigned. The linear score is the linear transformation of the NSAA score to a scale of 0 to 100 [Mayhew 2013].

Total scores and linear scores from the North Star Ambulatory Assessment will be summarized by visit and change from baseline to each post baseline visit will be summarized descriptively for ambulatory subjects with non-missing baseline NSAA assessments. Similarly the total and linear scores will also be summarized for each actual age.

The number and proportion of loss of function of each North Star Ambulatory Assessment item at week 48 will be tabulated. The function loss defined as a shift from non-zero at baseline to zero at week 48. The missing data will be handled by last observation carried forward (LOCF).

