7.2.1.3. End of Treatment

It is planned that each subject will return to the clinical research facility at Week 240 (Visit 22) for the End-of-Treatment Visit. However, this study duration may be altered per the conditions noted in Section 6.2.1. In this case, the timing of the End-of-Treatment Visit, will be adjusted appropriately. If the patient terminates the study early because ataluren is commercially available in that country, then the patient only needs to return for the End-of-Treatment Visit.

If the subject discontinues prematurely, except patients switching to commercial ataluren (ie, before Week 240) and the last visit to the investigator site occurred >3 weeks previously, the procedures that would normally be performed at Week 240 should be performed as a Premature Discontinuation Visit before the subject leaves the study.

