7.2.18. North Star Ambulatory Assessment

The NSAA will be used to evaluate physical function in those patients who are ambulatory at study entry, using standardized procedures (see Study Manual). The NSAA will be performed at Screening (Visit 1), Week 48 (Visit 6), Week 96 (Visit 10), Week 144 (Visit 14), Week 192 (Visit 18) and Week 240 (Visit 22 End-of-Treatment/Premature Discontinuation).

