6 DATA HANDLING

6.1 Analysis Visits based on Visit Windows

Since some subjects had early terminations or unscheduled visits in during, the derived analysis visits will be generated by visit window defined as follows.

The derived visits will be generated by visit window defined as follows.

Let ADY=assessment date –first dose date +1.

```
IF .<= ADY <=1 THEN AVISIT= BASELINE AND AVISITN=1;
IF 42<= ADY <=126 THEN AVISIT=WEEK 12 AND AVISITN=2;
IF 126<ADY <=210 THEN AVISIT=WEEK 24 AND AVISITN=3;
IF 210<ADY <=294 THEN AVISIT=WEEK 36 AND AVISITN=4;
IF 294<ADY <=378 THEN AVISIT=WEEK 48 AND AVISITN=5;
IF 378<ADY <=462 THEN AVISIT=WEEK 60 AND AVISITN=6;
IF 462<ADY <=546 THEN AVISIT=WEEK 72 AND AVISITN=7;
IF 546<ADY <=630 THEN AVISIT=WEEK 84 AND AVISITN=8;
IF 630<ADY <=714 THEN AVISIT=WEEK 96 AND AVISITN=9;
IF 714<ADY <=798 THEN AVISIT=WEEK 108 AND AVISITN=10;
IF 798<ADY <=882 THEN AVISIT=WEEK 120 AND AVISITN=11;
IF 882<ADY <=966 THEN AVISIT=WEEK 132 AND AVISITN=12;
IF 966<ADY <=1050 THEN AVISIT=WEEK 144 AND AVISITN=13;
IF 1050<ADY <=1134 THEN AVISIT=WEEK 156 AND AVISITN=14;
IF 1134<ADY <=1218 THEN AVISIT=WEEK 168 AND AVISITN=15;
IF 1218<ADY <=1302 THEN AVISIT=WEEK 180 AND AVISITN=16;
IF 1302<ADY <=1386 THEN AVISIT=WEEK 192 AND AVISITN=17;
IF 1470<ADY <=1554 THEN AVISIT=WEEK 216 AND AVISITN=19;
IF 1554<ADY <=1638 THEN AVISIT=WEEK 228 AND AVISITN=20;
IF 1638<ADY <=1722 THEN AVISIT=WEEK 240 AND AVISITN=21
IF 1722<ADY <=1806 THEN AVISIT=WEEK 252 AND AVISITN=22
IF 1806<ADY <=1890 THEN AVISIT=WEEK 264 AND AVISITN=23
IF 1890<ADY <=1974 THEN AVISIT=WEEK 276 AND AVISITN=24
IF 1974<ADY <=2058 THEN AVISIT=WEEK 288 AND AVISITN=25
IF 2058<ADY <=2142 THEN AVISIT=WEEK 300 AND AVISITN=26
```

IF 2142<ADY <=2226 THEN AVISIT=WEEK 312 AND AVISITN=27

IF 2226<ADY <=2310 THEN AVISIT=WEEK 324 AND AVISITN=28

IF 2310<ADY <=2394 THEN AVISIT=WEEK 336 AND AVISITN=29.

If there are more than 1 valid assessment within one visit window, the last one will be chosen as the analysis value.

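### SAP 5.8.3: with no NSAA scheduled between Screening and Week 48, LOCF can fill the Week 48 item-loss table with baseline values, which count as no loss by construction

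*SAP*

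**What the plan says.** SAP 5.8.3 sets the definition, "The function loss defined as a shift from non-zero at baseline to zero at week 48", and then the missing-data rule, "The missing data will be handled by last observation carried forward (LOCF". It does not say whether the baseline value itself may be carried into the Week 48 cell, or what the denominator is. Under SAP 6.2, baseline is the last valid value on or before the first dose, which for the NSAA is normally Screening.

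Protocol 7.2.18 gives the schedule: "The NSAA will be performed at Screening (Visit 1), Week 48 (Visit 6), Week 96 (Visit 10", and so on every 48 weeks. The schedule tables in both documents agree.

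Three other provisions bear on the point:
- **Zero-score rule (SAP 5.8.3):** "If an activity cannot be performed due to disease progression/loss of ambulation, a score of zero will be assigned".
- **Discontinuation assessment (Protocol 7.2.18 and 7.2.1.3):** the last NSAA time point is "Week 240 (Visit 22 End-of-Treatment/Premature Discontinuation". For a boy who leaves early and whose last site visit was more than 3 weeks before, "the procedures that would normally be performed at Week 240 should be performed as a Premature Discontinuation Visit before the subject leaves the study".
- **Visit window (SAP 6.1):** "IF 294<ADY <=378 THEN AVISIT=WEEK 48 AND AVISITN=5".

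**The concern.** LOCF needs an intermediate observation to carry. Here none is scheduled. When Screening is the last value, the rule compares baseline with itself. A non-zero item stays non-zero, so a loss cannot be recorded.

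The protocol describes DMD as progressive, and Protocol 13.2.6.3 says that the abilities the NSAA measures deteriorate without treatment. A missing item is therefore not good evidence of a kept item. In a single-arm study a lower loss proportion reads as favourable to ataluren, and a reader of the table would not see how many of the kept items were filled from Screening.

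**Working it through.** The plan gives no item-loss rate, missing rate or number of ambulatory boys for this table, so there is no figure to reproduce. The check has two parts.

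**1. Which items end up with baseline carried forward?** Consider items that were non-zero at baseline.

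| Situation | Governing text | Entry in the table |
|---|---|---|
| Item observed on days 295–378 (day 336, −41/+42) | SAP 6.1 | As observed |
| Item not performable because of disease | SAP 5.8.3 zero-score rule | Loss |
| Item skipped for another reason at an attended Week 48 visit | LOCF | Screening value: no loss |
| Whole NSAA missed, boy stays on study | LOCF | Screening value: no loss, unless an unscheduled NSAA exists |
| Boy leaves early with a discontinuation NSAA on days 42–294 | Protocol 7.2.1.3 and 7.2.18; SAP 6.1 labels it Week 12, 24 or 36 | Discontinuation value |
| Boy leaves within 3 weeks of a Week 12, 24 or 36 visit | Discontinuation visit not required by 7.2.1.3; evaluations only encouraged by Protocol 9 | Screening value: no loss, if no NSAA is done |
| First post-baseline NSAA after day 378 | SAP 6.1 labels it Week 60 or later | Screening value: no loss |
| NSAA only on days 2–41 | No analysis visit in SAP 6.1 | Unclear |
| Whole NSAA not done because of disease | Zero-score rule speaks of an activity, not a missed visit | Unclear |

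The third row shows an inconsistency within one section. For 13 to 16 performed activities, the total score is prorated by 17/x. The item table fills the same gap from Screening.

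**2. How large is the effect?** All rates here are assumptions. Let p be the true loss risk, m the share of items with no usable Week 48 value, f the share of those whose last value is Screening, and b = m × f.

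With equal risk in missing and observed items, and any other carried value reflecting Week 48 status:

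reported = p × (1 − b), so the relative understatement is b, whatever p is.

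| True p | b = 5% | b = 10% | b = 20% |
|---|---|---|---|
| 10% | 9.5% | 9.0% | 8.0% |
| 20% | 19.0% | 18.0% | 16.0% |
| 30% | 28.5% | 27.0% | 24.0% |

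The discontinuation NSAAs matter. With p = 20% and m = 10%, f = 1 gives 18.0%, f = 0.5 gives 19.0%, and f = 0 gives 20.0%.

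If missing items carry twice the risk (20% observed, 40% missing, b = 20%):
- truth = 0.8 × 0.20 + 0.2 × 0.40 = 24%
- LOCF = 0.8 × 0.20 = 16%
- observed cases only = 20%
- missing counted as loss = 0.8 × 0.20 + 0.2 = 36%

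The last case in counts, for an assumed 50 boys with 10 missing and 8 observed losses: LOCF 8/50 = 16%, observed 8/40 = 20%, missing as loss 18/50 = 36%.

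**The case against.** The strongest reply is that the SAP says only LOCF. If that means post-baseline values only, a boy with none drops out and is not scored as having kept the item. The zero-score rule already takes the most informative gaps out of LOCF, the discontinuation NSAA supplies a later value for many who leave, and the Week 48 window accepts visits about six weeks either side. The table has no test, the listed NSAA endpoint is change from baseline, and item loss is not among the natural-history comparisons in SAP 8.2.1.

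Most of this stands as a limit on size. It does not remove the problem. A boy who stays on study but misses the assessment, one who leaves shortly after a visit without an NSAA, and an item skipped for a reason other than disease all remain exposed. If baseline may not be carried, LOCF has almost nothing to carry and the denominator is undefined, so the text needs correcting on either reading.

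A reader might infer that every boy without a Week 48 NSAA is scored as no loss, or that the whole table is certain to favour ataluren. The documents do not support either. Some boys will have a later NSAA or a zero score, and a zero recorded at early discontinuation is carried forward as a loss. The direction is certain only for items filled from baseline, and how many there are is not known.

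**Conclusion.** Applied as written, the rule makes loss impossible to record for any item whose last value is Screening, and for those items the proportion can only be understated. The relative understatement equals the share of items filled from baseline, assuming equal loss risk; it is larger if missing items are more often lost, which is plausible in this disease but not documented.

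The actual size cannot be determined. At p = 20% and b = 10%, the gap of 2 percentage points is one boy per item among 50, and about two among 96, the most the study plans to enrol in total. The conclusion also assumes that LOCF is read as allowing baseline to be carried, which the SAP leaves open. The consequence is confined to one descriptive table of a secondary variable. The LOCF sentence is attached to that table, and 5.8.3 states no carry-forward for the total and linear scores.

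**What to change.** Amend SAP 5.8.3 as follows:
- Do not carry baseline forward into the Week 48 item-loss table.
- Report loss as n/N among boys with a post-baseline value for that item in the Week 48 window, and give the number missing per item.
- State that the existing zero-score rule also applies when the whole assessment is not done because of disease progression or loss of ambulation.
- Add a sensitivity row that counts the remaining missing items as loss.

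The two rows bracket the loss rate provided that missing items are lost at least as often as observed ones. They do not correct it: in the informative example above, they show 20% and 36% around a truth of 24%.

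The cost is SAP wording only, with no new data. The denominator is slightly smaller and the figure slightly less favourable. NSAAs taken at discontinuation before day 295 leave the main row, so those items appear in the number missing and in the sensitivity row.

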5.8.4 Egen Klassifikation Scale

The total score of EK scale and change from baseline to each post baseline visit will be summarized descriptively by visit for non- ambulatory subjects and As-Treated population. Similarly the total score will also be summarized for each actual age.

5.8.5 Spirometry

Pulmonary function parameters of %-predicated FVC, %-predicted FEV1 (adjusted using ulna length and age), peak expiratory flow (PEF), and peak cough flow (PCF) and their absolute and relative changes from baseline will be summarized by visit for non- ambulatory subjects and As-Treated population. Similarly the observed values of the endpoints will also be summarized for each actual age.

The Kaplan-Meier method will be applied to the analysis of age at FVC <1 liter. The median age at FVC<1 liter will be reported by corticosteroids use at baseline. The Kaplan-Meier curves will also be displayed. The age at FVC<1 liter is the one at the first time FVC<1 liter. If subjects do not have FVC<1 liter, the age at the last non-missing FVC assessment will be chosen as the censor age.

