5.9.2 Corticosteroids type subgroups

The by-visit summary on the observed values and change from baseline to each post baseline visit values will be performed descriptively for each corticosteroid type prior to study entry (deflazacort vs prednisone/prednisolone) on 6MWT and TFTs. The Kaplan-Meier method will be applied to the analysis of age at loss of ambulation and age at FVC <1 liter each subgroup.

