8.2 Matched Populations

To compare CINRG with Study 019, the matched populations are defined in the following table for different endpoints and analyses. Matching criteria will be adjusted if imbalance demographics and baseline characteristics are observed.

Endpoint/ Analysis	Age (Years) at Study Entry	Age (Years) at Assessment	Steroid Use	Ambulation status	Exclude EXON 51 and 45	Baseline value	Visit Year
Age at loss of ambulation	9-18	Not applicable	Cumulative Steroid use duration at study entry ≥ 12 months	Ambulatory at study entry	Yes	time taken to run/walk 10 meters 3.5-26.4 seconds ²	Not applicable
Age at FVC <1 liter	9-18	Not applicable	Not applicable	Non- ambulatory at study entry	Yes	1-3.08	Not applicable
Piece-wise regression based on FVC	Not applicable	≤ 22	Cumulative Steroid use duration at each assessment ≥ 24 months	Non- ambulatory at each assessment	Yes	Not applicable	≥ 2012
%- predicted FVC	9-21	Not applicable	Not applicable	Non- ambulatory at study entry	Yes	32.6- 110.3	Not applicable
%- predicted FEV1	9-21	Not applicable	Not applicable	Non- ambulatory at study entry	Yes	28.1- 104.0	Not applicable
PEF	9-21	Not applicable	Not applicable	Non- ambulatory at study entry	Yes	1.3-218.0	Not applicable
EK	9-18	Not applicable	Not applicable	Ambulatory at study entry	Yes	Score 0-15	Not applicable
6MWT	9-18	Not applicable	Cumulative Steroid use duration at study entry ≥ 12 months s	Ambulatory at study entry	Yes	36-553 meters	Not applicable
time taken to run/walk 10 meters	9-18	Not applicable	Cumulative Steroid use duration at study entry ≥ 12 months	Ambulatory at study entry	Yes	3.5-26.4 seconds	Not applicable
time taken to stand from supine	9-18	Not applicable	Cumulative Steroid use duration at study entry ≥ 12 months	Ambulatory at study entry	Yes	2.3-30 seconds	Not applicable
NSAA	9-18	Not applicable	Cumulative Steroid use duration at study entry ≥ 12 months s	Ambulatory at study entry	Yes	Total score 3-34	Not applicable

8.2.1 Analyses Based on Matched Populations of CINRG and Study 019

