In Study 019, the loss of ambulation is defined as the disease progression reported as the adverse event or the time to run/walk 10 meters > 30 seconds, whichever occurs earlier. The event age is the one on the AE start date. The subjects who are ambulatory at the end of study will be censored on the last valid timed function tests assessment date. Age on that date will be used in the analysis. In the CINRG data, the age at the earliest report of the non-ambulation or the time to run/walk 10 meters > 30 seconds, whichever earlier, will be picked as the event age. If subjects in CINRG data do not report non-ambulation, the age at the last report of ambulation will be chosen as the censor age. A sensitivity analysis will be performing based on the loss of ambulation defined only by disease progression AE.

Similarly, the age at FVC < 1 liter is the one at the first time FVC < 1 liter. If subjects do not have FVC < 1 liter, the age at the last non-missing FVC assessment will be chosen as the censor age.

For CINRG data only, the observed values will be summarized descriptively for each actual age on 6MWT, time to run/walk 10 meters, time to stand from supine, NSAA total and linear scores, %-predicted FVC, %-predicted FEV1, PEF and EK total scores by corticosteroid use at baseline (yes or no) and overall based on the matched populations.

NSAA score derivation algorithms in Study 019 will be applied to CINRG data.

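### SAP 5.8.5 dates the FVC <1 liter event at the first test for boys who are already below 1 liter, so the median age can partly reflect age at enrolment

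*SAP*

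**What the plan says.** SAP 5.8.5 names the estimator: "The Kaplan-Meier method will be applied to the analysis of age at FVC <1 liter". The event age is defined as follows: "The age at FVC<1 liter is the one at the first time FVC<1 liter". The only censoring rule is for boys who never fall below the threshold: "If subjects do not have FVC<1 liter, the age at the last non-missing FVC assessment will be chosen as the censor age". The output is a median by steroid group: "The median age at FVC<1 liter will be reported by corticosteroids use at baseline". SAP 5.9.2 reuses the endpoint by steroid type ("The Kaplan-Meier method will be applied to the analysis of age at loss of ambulation and age at FVC <1 liter each subgroup"), and SAP 5.9.3 does so by cumulative steroid duration.

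The CINRG comparison repeats the definition in SAP 8.2.1: "the age at FVC < 1 liter is the one at the first time FVC < 1 liter". In the matching table of SAP 8.2, however, the row "Age at FVC <1 liter" admits only boys aged 9-18 who are nonambulatory at entry with a baseline value of 1-3.08. No unit is printed; liters are implied. The table can change: "Matching criteria will be adjusted if imbalance demographics and baseline characteristics are observed".

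Protocol 7.2.20 gives spirometry to nonambulatory patients at Screening and every 24 weeks. Protocol 4.2 and 4.3 set no minimum FVC.

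**The concern.** For a boy whose first FVC is already below 1 liter, that test shows that he has crossed the threshold but not when. His crossing age is left-censored at the first-test age. SAP 5.8.5 treats that age as an exact event.

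How late he is dated depends on when he joined the study. If such boys are present, the median age mixes disease course with enrolment age. This matters most for the comparisons by steroid use, type and duration. Two groups with the same true course but different enrolment ages can show different medians. The within-study median of 5.8.5 and the matched Study 019 median of 8.2.1 can also differ because one at-risk set includes these boys and the other does not. SAP Section 7 does not mention this.

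**Working it through.** The documents give no event count or median for this endpoint, so there is no planned figure to reproduce.

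**Step 1: can a boy enter below 1 liter?** Nothing in eligibility prevents it. The %-predicted FVC row of SAP 8.2 runs from 32.6 to 110.3. A boy at 32.6% is below 1 liter whenever his predicted FVC is under 1/0.326 = 3.07 liters. This shows that it is possible, not that it happened.

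**Step 2: dating error for one boy.** A boy first seen at 1 liter or more is dated late by at most one test interval, 24/52.18 = 0.46 year, if no visit is missed. A boy already below is dated late by (first-test age minus crossing age), which the plan does not bound. If FVC falls by a constant 5% to 10% a year (an assumption), the delay is ln(1/FVC)/rate:
- 0.8 liter: 0.223/0.10 = 2.2 years to 0.223/0.05 = 4.5 years
- 0.9 liter: 0.105/0.10 = 1.1 years to 0.105/0.05 = 2.1 years

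**Step 3: effect on the median.** Simulation of 20,000 boys per setting. From the documents: tests every 24 weeks and follow-up of 240 weeks. Assumed: crossing age normal with SD 3, and entry age uniform and independent of crossing age. The entry range is 9-21 years (pulmonary rows of SAP 8.2) or 9-18 years (the row for this endpoint). Medians in years, with simulation noise of about 0.1:

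| Entry | True | Literal 5.8.5 | Literal minus true | Exclude, no entry time | Exclude, delayed entry |
|---|---|---|---|---|---|
| 9-21 | 17 | 18.5 | 1.5 | 18.5 | 17.3 |
| 9-21 | 18 | 19.1 | 1.1 | 19.4 | 18.3 |
| 9-21 | 20 | 20.4 | 0.4 | 21.0 | 20.3 |
| 9-18 | 17 | 17.4 | 0.4 | 18.0 | 17.3 |
| 9-18 | 18 | 18.0 | 0.0 | 18.8 | 18.2 |
| 9-18 | 20 | 20.1 | 0.1 | 20.4 | 20.2 |

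With entry at 9-21, 15% to 34% of boys are already below 1 liter at first test, and they supply 31% to 49% of events. Left-censoring them with an interval-censored estimator gives a median within about 0.2 year of the truth in all six settings.

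**Step 4: two groups with the same true median of 16.** One group enters at 9-15 years and the other at 13-19.

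| Method | Entry 9-15 | Entry 13-19 | Gap |
|---|---|---|---|
| Literal 5.8.5 | 16.1 | 17.5 | 1.4 |
| Exclude, delayed entry | 16.3 | 17.2 | 0.9 |
| Interval-censored | 16.1 | 16.2 | 0.1 |

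At a true median of 18 the literal gap is about 0.4 year.

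**The case against.** The strongest reply is that the rule may affect nobody. The number of Study 019 boys with a first FVC below 1 liter is not given, and the lower limit of 1 in SAP 8.2 could be a chosen threshold or simply an observed minimum. This stands: the flaw is in the rule, and its effect is unknown.

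The second reply is that consequence is low. SAP 3.3 lists % predicted FVC and FEV1, not age at FVC <1 liter. The study has no formal hypothesis, and 5.8.5, 5.9.2 and 5.9.3 plan no test. The log-rank comparison with CINRG already uses the restricted baseline range. This also stands and limits the severity.

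Third, with entry at 9-18, the range printed for this endpoint, the literal median is hardly off. That is correct for the overall median. But 9-18 is a matching criterion for the CINRG comparison, and 5.8.5 sets no age limit. Nor does a small overall shift protect subgroups that enrolled at different ages.

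A reader might infer that the SAP holds two incompatible event definitions. It does not: 8.2.1 repeats the wording of 5.8.5, and 8.2 changes only who is at risk. A whole-cohort summary and a matched subset are expected to differ. What is missing is a statement that they differ in this way.

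The constant 5% to 10% decline in Step 2 is in neither document, and SAP 8.2.1 itself models log FVC with a changepoint. Those delays are illustrations only.

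**Conclusion.** The concern holds on the text. SAP 5.8.5 records a left-censored crossing as an exact event, always too late for the boy concerned. For the median, the size rests on assumptions. It is nil if no boy was below 1 liter at first test. Otherwise, with crossing-age SD 3 and true medians of 17 to 20, the literal median is 0.4 to 1.5 years too old with entry at 9-21, and 0.4 or less with entry at 9-18.

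Two stronger readings are not supported. One is that the reported median must be materially too old: with entry at 9-18 and a true median of 18, the simulated error is 0.0. The other is that a particular steroid group is favored: the documents give no enrolment ages by steroid group, so only the mechanism is shown.

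The point is minor to moderate: worth changing, for a descriptive endpoint.

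**What to change.** In SAP 5.8.5, 5.9.2 and 5.9.3:
- Keep all boys. Treat those whose first FVC is below 1 liter as left-censored at their first-test age, and use an interval-censored (Turnbull) estimator in place of plain Kaplan-Meier.
- Report how many boys were below 1 liter at first test, overall and in each subgroup. The count alone shows whether the issue matters.
- As a secondary option, limit the analysis to boys whose first FVC is 1 liter or more, with delayed entry at the age of first FVC. In Step 4 this narrows the spurious gap but does not remove it.
- Do not copy the baseline restriction of 8.2 without an entry time. In Step 3 that gives a median no better than the literal rule in any setting, and worse in five of six.
- State that the medians of 5.8.5 and 8.2.1 use different at-risk sets.

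The cost is a few sentences in the SAP, some programming and wider uncertainty around the medians. The left-censored analysis also assumes that enrolment age is unrelated to crossing age, and the SAP should say so.
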